7.10.2 Outliers

No outliers will be excluded from the analyses.

7.10.3 Visit Windows

All data collected up to 1-year post-transplant (i.e., day 380) will be included in the analysis, unless otherwise specified, except for mortality which is restricted to deaths occurring up to day 365 following the transplant. All data collected up to day 190 will be included in the 6-month post-transplant analyses, except for mortality which is restricted to deaths occurring up to day 180 following the transplant.

For efficacy analysis, data will be analyzed from the transplant day (day 0); for safety analysis, data will be analyzed from the first injection of study drug.

The summary by visits will follow the visits according to the CRF.

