**Table 1 Schedule of Assessments – Primary Study Period Visit 1 (Screening) – Day 365**

	Screening 	Dose 1  (Baseline)		Transplant 	Dose 2		Dose 3		Dose 4		Dose 5			Primary Study Period Completion / Early Termination Visit 	
Visit Number	V1 	V2 	V3 	V4	V5 	V6 24*	V7	V8	V9	V10*	V11	V12*	V13	V14	
Day Relative to Transplant or Prior Dose	-30 to -5	-14 to -3	Follow-up Dose 1 +10 to 14 days	0	14-40	Follow-up Dose 2 +10 to 14 days	60	Follow-up Dose 3 +10 to 14 days	90	Follow-up Dose 4 +10 to 14 days	100	180	Follow-up Dose 5 +10 to 14 days	270	365
Visit Window							±5 days		±10 days			±10 days		±10 days	+ 14 days (between Day 365 to 379)
Month	-1			0	1		2		3			6		9	12
Assessments															
Informed Consent 	X														
Subject Number Assignment 	X														
Inclusion/Exclusion Assessment	X	X P													
Medical History & Demographics	X	X P													
Clinical Evaluation (Physical Exam & Vitals) 	X	X P			X P		X P		X P			X P		X	X
Concomitant Medication Review 	→														
Safety Laboratory 	X	X			X P	X	X P	X	X P	X		X P	X		
CMV Screening Serology 	X														
Modified HCT-CI Score 	X														
Pregnancy Test (females) 	X	X P			X P		X P		X P			X P		X	X
Adverse Event and SAE Review 	→														
Randomization		X P													
Health Economic Assessment (HEA)	→														
EQ-5D, FACT-BMT, WPAI 		X P			X P		X P		X P			X P		X	X
Immunogenicity Laboratory 		X P			X P			X	X P			X P			X

Table continued on next page

	Screening 	Dose  (Baseline)		Transplant 	Dose 2		Dose 3		Dose 4		Dose 5			Primary Study Period Completion / Early Termination Visit 	
Visit Number	V1 	V2 	V3 	V4	V5 	V6 24*	V7	V8	V9	V10*	V11	V12*	V13	V14	

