24. If the subject does not meet the criteria for dosing by day 40, V5 procedures (except study drug injection and local reactogenicity assessment) need to be completed within 5 days of day 40 (day 40 to 45) and V6 should be skipped.
25. The day 365 visit must occur on day 365 +14 days (between day 365 to 379); it cannot occur prior to day 365 for subjects who do not prematurely withdraw from both treatment and continued follow-up. For a subject who prematurely withdraws from the study (discontinues treatment with no continued follow-up), the study completion visit is to be completed within 14 days of study withdrawal.

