## **7.10 Handling of Missing Data, Outliers, Visit Windows, and Other Information**

In the analysis of the primary endpoint, subjects with unknown survival status will be assumed to have had the primary endpoint. Sensitivity analysis excluding those subjects from the denominator will be conducted. Other imputations of missing data will be considered based on the nature and quantity of missing data with appropriate statistical methods which will be fully specified prior to unblinding. Assignments of observations to visits for analyses by scheduled visit will be based on dates relative to date of transplantation. The details will be described in the SAP.

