24. If the subject does not meet the criteria for dosing by day 40, V5 procedures (except study drug injection and local reactogenicity assessment) need to be completed within 5 days of day 40 (day 40 to 45) and V6 should be skipped.
25. The day 365 visit must occur on day 365 +14 days (between day 365 to 379); it cannot occur prior to day 365 for subjects who do not prematurely withdraw from both treatment and continued follow-up. For a subject who prematurely withdraws from the study (discontinues treatment with no continued follow-up), the study completion visit is to be completed within 14 days of study withdrawal.

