7.4.3.1 Analyses of Clinical Outcomes Exploratory Endpoints

The following exploratory endpoints will be analyzed by incidence and/or time to event approach by treatment group.

For the endpoint of adjudicated CMV EOD, and Investigator-reported CMV EOD, the summary will include incidence (i.e., number of episodes) where all events are added in addition to the number and percentage of subjects with at least one event. The proportion of subjects with an event will be analyzed by the CMH method and the odds ratio, its 95% CI and p-value will be calculated.

- Composite endpoint of all-cause mortality and adjudicated CMV EOD at 6 months post-transplant, using the same CMH approach as the primary endpoint. Deaths occurring up to day 180 from transplant will be counted. In other words deaths occurring on or before 180 days after transplant will be counted, although the death could be reported later. Patients with CMV EOD that is assessed by the independent and blinded adjudication committee will be counted for the events that are observed up to day 190 from transplantation.

- All-cause mortality at 6 months post-transplant using time to event method, as described in Section 7.4.1.2. Deaths occurring up to day 180 from transplant will be counted. In other words deaths occurring on or before 180 days after transplant will be counted, although the death could be reported later.
- Relapse mortality (death due to relapse of the subject's primary disease), using the same CMH approach as the primary endpoint.
- Non-relapse mortality (death due to causes unrelated to the subject's primary disease), using the same CMH approach as the primary endpoint.

The proportion and number of subjects the events below will be descriptively summarized.

- Proportion of grade 3-4 aGVHD
- Proportion of engraftment (Yes/No)
- Proportion of graft rejection/poor graft function
- Proportion of relapse of primary disease requiring therapy

Additionally, number (percentage) of subjects by taking the maximum grade of aGVHD will be summarized.

Karnofsky Performance Scale (KPS) scores are collected at baseline and post-baseline. KPS scores will be descriptively summarized at baseline and the visits specified in schedule of assessments (Table 1), but KPS scores at any additional visits will only be listed.

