7.4.3.2 Duration of Hospitalization, Health Economic, and Quality of Life Variables

Duration of hospitalizations, and days in emergency room, in days per year will be compared between treatments using descriptive statistics.

The number of emergency room visits, and Non-protocol-related physician visits, also will be compared between treatments using descriptive statistics.

The EQ-5D dimensions will be summarized as categorical variables by treatment arm at each visit and at final visit. Change from baseline in the EQ-5D VAS score will be summarized by treatment arm at each visit and at Final visit.

Total FACT-BMT and the corresponding changes from baseline will be summarized by treatment arm at each visit and at Final Visit.

The percent activity impairment due to health from the WPAI: GH and corresponding changes from baseline will be summarized by treatment arm at each visit and at Final Visit.

Treatments will be compared with respect to each of these scales using analysis of covariance (ANCOVA) of change from baseline to final visit with treatment, donor-recipient relatedness, and donor CMV serostatus as factors and baseline value as a covariate.

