7.4.3.3 Immunogenicity Variables

T-cell responses to pp65 and gB-specific antibody levels will be summarized by visit and treatment group on the original scale. A plot of each of the immune responses over time by treatment will be produced. The comparisons between treatments will be made at each measurement visit using Wilcoxon rank sum test without adjusting for the multiplicity on the original scale. In addition, each of the immune response variables post baseline on the 10 based log scale will be analyzed using repeated measures model, where the randomization stratum, treatment, time, and treatment by time interaction will be the explanatory variables. The self-consistent sandwich correlation structure will be used. If the test for the time by treatment interaction is significant (p value <0.1) the overall treatment group comparison will not be displayed in the plots.

As an exploratory analysis, the relationship between immunogenicity variables and treatment outcome will be assessed using logistic regression method. The treatment outcome is if subject is free of CMV viremia through one year post-transplant. The optimal cutoff values of the respective immunogenicity variables that will define the treatment outcome will be explored in terms of maximizing the area under the receiver operating characteristic (ROC) curves.

All analyses of immunogenicity variables will be based on the IAS.

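### The SAP assigns by-visit data by CRF label where the protocol requires dates, so early-termination values can enter the V14/day-365 results unless the CRF labels them separately

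*SAP*

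**What the plan says.** - **Protocol 7.10** gives a date rule and leaves the details to the SAP: "Assignments of observations to visits for analyses by scheduled visit will be based on dates relative to date of transplantation".
- **SAP 7.10.3**, the section on visit windows, gives a label rule: "The summary by visits will follow the visits according to the CRF". The only date limits there and in SAP 7.1 and 7.4.3 are upper ones: day 380 for data collected at visits and day 365 for deaths, with day 190 and day 180 for the 6-month analyses.
- **Table 1 in both documents** heads the V14 column "Primary Study Period Completion / Early Termination Visit", with day 365 beneath it.
- **Footnote 25 to that table** says of a V14 before day 365 that "it cannot occur prior to day 365 for subjects who do not prematurely withdraw from both treatment and continued follow-up". For a subject who does withdraw from both, "the study completion visit is to be completed within 14 days of study withdrawal".
- **By-visit analyses that reach V14:**
  - Immunogenicity (SAP 7.4.3.3): "The comparisons between treatments will be made at each measurement visit using Wilcoxon rank sum test", together with plots over time and a repeated-measures model with time and treatment-by-time terms.
  - Quality of life (SAP 7.4.3.2), for example: "Total FACT-BMT and the corresponding changes from baseline will be summarized by treatment arm at each visit and at Final Visit".
  - Karnofsky (SAP 7.4.3.1): "KPS scores will be descriptively summarized at baseline and the visits specified in schedule of assessments".
  - Vital signs (SAP 7.5.4): summarised by treatment group and visit.

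**The concern.** A date rule and a label rule give the same answer only if each label means one time point. V14 does not. For a completer it means day 365 to 379; for a subject who leaves the study it can mean any day after transplant. With no lower date limit, the SAP offers nothing that separates the two.

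At stake is the meaning of the V14 row. If early values sit in it, a result presented as the 1-year comparison mixes two times since transplant, and the early values come from subjects who stopped, possibly after fewer doses. If early termination differs between arms, the V14 contrast is biased in a direction that cannot be foretold. If it does not differ, the contrast is blurred. Day 365 is of some interest here: Protocol 1.3.2.2 reports the phase 2 gB antibody difference as significant at that time (P = 0.009), although the phase 2 repeated-measures comparison over days 56 to 365 was not (P = 0.749).

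**Working it through.** The plan gives no figure on this point, and the sample-size calculation does not bear on it. The check is mainly one of setting the texts side by side.

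**1. Are the two rules different?** Yes. Protocol 7.10 assigns by date; SAP 7.10.3 assigns by CRF visit. SAP 7.1 does define an analysis day counted from transplant, but no SAP section uses it to place an observation in a scheduled visit.

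**2. Can a V14 record be early?** Yes. The column is shared, and the bar on attending before day 365 covers only subjects who do not leave both treatment and follow-up. As an example, a subject who withdraws on day 50 may attend up to 14 days later: 50 + 14 = 64, and 365 − 64 = 301 days before the nominal time.

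**3. What is collected there?** Table 1 marks V14 for immunogenicity, EQ-5D/FACT-BMT/WPAI, Karnofsky and clinical evaluation including vital signs. Central safety laboratory tests are not scheduled at V14.

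**4. Which analyses use the label?**

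| Analysis | Placed by | Affected? |
|---|---|---|
| Primary composite (SAP 7.4.1) | event dates, day 365/380 limits | No |
| Viremia and antiviral therapy (7.4.2.1, 7.4.2.2) | event dates, day 380 limit | No |
| Mortality (7.4.2.3.3) | date of death, day 365 limit | No |
| ANCOVA of change to final visit (7.4.3.2) | last visit, whatever its label | No |
| Immunogenicity tests, plots, repeated-measures time factor (7.4.3.3) | visit | Yes, at V14 |
| By-visit EQ-5D, FACT-BMT, WPAI (7.4.3.2) | visit | Yes, at V14 |
| Karnofsky (7.4.3.1), vital signs (7.5.4) | visit | Yes, at V14 |

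In the immunogenicity model the V14 values also enter the treatment-by-time test, which at P < 0.1 decides whether the overall comparison appears on the plots.

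**5. What share of V14 records could be early?** The documents do not say, so this is illustration only. Let *w* be the proportion of dosed subjects who leave alive and attend an early visit, and *d* the proportion with no V14 record. The early share of V14-labelled records is then *w* / (1 − *d*). *w* is assumed. For *d* I take the phase 2 composite rates in SAP section 4, 22.5% and 35.3%, as a rough stand-in for death; they also count survivors with CMV end organ disease.

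| *w* (assumed) | *d* = 22.5% | *d* = 35.3% |
|---|---|---|
| 2% | 0.02 / 0.775 = 2.6% | 0.02 / 0.647 = 3.1% |
| 5% | 0.05 / 0.775 = 6.5% | 0.05 / 0.647 = 7.7% |
| 10% | 0.10 / 0.775 = 12.9% | 0.10 / 0.647 = 15.5% |
| 15% | 0.15 / 0.775 = 19.4% | 0.15 / 0.647 = 23.2% |

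These are shares of records. They do not convert into a bias in any treatment comparison, because the documents give no early and late values to compare.

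**The case against.** **The CRF may already solve this.** SAP 7.10.3 defers to the CRF, and the CRF is not supplied. A separate early-termination page or visit name would keep early values out of V14, and a shared column in a schedule does not prove a shared label in the database. A reader might infer that early values will certainly be analysed as day 365; the documents do not support that. The point is conditional on the CRF. It remains true that the SAP mentions no separate label, and that the protocol's date rule would hold whichever way the CRF is built.

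**Few subjects may be involved.** Under Protocol 3.5, subjects who stop treatment only stay on the schedule apart from the dose follow-up visits, and those who cannot comply are asked to attend the scheduled V14. Withdrawal of consent ends follow-up except for mortality from public records, although the same section asks for a completion visit within 14 days. Deaths yield no early visit. T-cell samples are not drawn when the lymphocyte count is known to be low. All of this stands, and it argues for the low end of any assumed range.

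**The outputs are minor.** Immunogenicity and quality of life are exploratory, the visit-wise Wilcoxon tests carry no multiplicity adjustment, and Karnofsky scores and vital signs are described only. This stands too.

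**The SAP's change log.** A reader might take its silence as a sign that the date rule was dropped without notice. The log in SAP 8.1 covers only changes from SAP Version 2 to 3.0, so it says nothing about when or why the SAP came to differ from the protocol.

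**Conclusion.** The protocol and SAP give different rules for placing observations in visits, and V14 is where the difference matters. Unless the CRF separates early termination from the day-365 visit, early values will enter the V14 results for immunogenicity, by-visit quality of life, Karnofsky scores and vital signs.

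The reach is limited to those exploratory or descriptive outputs. It would be wrong to read this as a threat to the trial's main efficacy conclusions. The size of any distortion cannot be derived: no early-termination rate is given, and neither is any early or 1-year value from which a bias could be worked out. It is still worth correcting before unblinding, because the remedy is cheap and the protocol already calls for it.

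**What to change.** In SAP 7.10.3, replace the CRF-label sentence with a rule for by-visit analyses:

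- V14 takes only values from day 365 to day 379, or to day 380 if the SAP's general cut-off is preferred.
- Early-termination values are shown in a separate Early Termination row or listed. Alternatively, they are mapped by study day, with a scheduled value taking precedence over a mapped one. That precedence rule is needed: the day-64 example falls in the V7 window (day 60 ± 5), where quality-of-life and Karnofsky values may already exist. Immunogenicity is not sampled at V7, so such a sample would only be listed.
- Visits anchored to a dose stay timed from that dose. V8, an immunogenicity visit, is set 10 to 14 days after dose 3 and has no window counted from transplant.
- Final Visit stays a separate category.

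Refer to this rule from SAP 7.4.3.1, 7.4.3.2, 7.4.3.3 and 7.5.4. If CRF labels are kept instead, state how the CRF identifies early termination and justify the departure from Protocol 7.10.

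The cost is a little wording and programming, and slightly fewer V14 records. Visit dates are already required in the source records (Protocol 8.1.2), so nothing is added for sites or subjects.

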8 DOCUMENT REVISION HISTORY

8.1 List of Changes in SAP Version 3.0 from Version 2

The changes from the approved SAP Version 2 (Dated 15-Dec-2015) to Version 3.0 that impact analyses are listed with the rationale in the table below.

SAP Sections	Description	Rationale
5.1, 5.2, 7.4.1.1	FAS is considered to be the primary analysis population	Consistency with protocol, and adherence to intent-to-treat principles.
5.3.1	Removed several reasons for exclusion from PPS	Deleted reasons that appear to be confounded with, or have little direct impact on, primary endpoint.
6.1.2.2	All-cause mortality at 1 year post-transplant was elevated from exploratory to secondary endpoint.	All-cause mortality is a component of the primary efficacy endpoint.
6.1.2.2, 7.4.2.3	A composite endpoint of CMV viremia and CMV-specific AVT use per the adjudication committee has been added	To address suspicion of potential CMV-specific infection
6.1.3, 7.4.3.1	Added exploratory endpoints: all-cause mortality at 6 months, and composite endpoint of all-cause mortality and adjudicated CMV EOD at 6 months post-transplant.	In order to evaluate efficacy around the time of the last planned injection.
6.1.3	Removed a few exploratory endpoints: -Incidence of severe cGVHD -Maximum cGVHD -Incidence of failure to engraft -Time to engraftment -Time to platelet recover -Time to grade 3 treatment emergent viral, bacterial, or fungal infections other than CMV	Limited clinical relevance
7.1	Clarification of '1-year post transplant' study period for death and non-death events.	Day 365 for mortality and Day 380 for visit-based assessments to allow for protocol-allowed visit window.
7.2.4	Previous and concomitant medication summaries switched from safety (e.g., SAF) to efficacy (e.g., FAS) populations.	Medications are summarized for potential confounding of efficacy results.
7.4.1.1, 7.4.1.2	Added 1-RR from CMH and 1-HR from Cox Model	Feedback from FDA

7.5	Safety overview and TEAE summary by SOC, HLT and PT for SAF, mSAF, xSAF	All safety assessment to be done for SAF and mSAF. Summary based on xSAF were limited to high-level summaries as the xSAF population includes a limited number of subjects.
7.5	Updated list of AE of Interest Removed: Malignancies, Sinusoidal Obstruction Syndrome Added: Systemic reactions, late onset reactions	Improve alignment with clinical objectives.

10 APPENDICES

Appendix 1: Handling of the Human Leukocyte Antigen (HLA) Mismatching

The HLA antigens are located on the cell surface. The genes encoding the HLA antigens are on chromosome 6 and have co-dominant expression: both alleles of one gene locus result in a surface HLA antigen. HLA class I antigens consist of a heavy chain and a β 2m unit and include the HLA-A, HLA-B and HLA-C antigens, while HLA class II antigens are constituted by two heavy chains and include the HLA-DR, HLA-DP and HLA-DQ antigens. All HLA genes (loci) are very polymorphic: each has various alleles (variants) that can be distinguished by DNA sequencing of gene DNA or by serological techniques for detection of the gene products (the HLA antigens on the cell surface): HLA typing.

The HLA types for HLA-A, HLA-B and HLA-DR are entered in the eCRF. Broad HLA types comprise of several fine specificities, the narrow types, but it is only the broad type codes (roughly equivalent to the serologically defined antigen or serotype (allotype)) that are entered into the eCRF.

Example:

Donor:	HLA A		HLA B		HLA DR	
	A11	A66	B5	-	DR5	DR6
Recipient:	HLA A		HLA B		HLA DR	
	A25	A32	B12	B5	DR5	DR7

Both codes for a locus will be considered identical (homozygote) if only one code is entered. In this case, the investigator will either enter the code twice or put a dash for the second entry (or leave the second entry blank). The order of the entries is unimportant. A mismatch between a donor and a recipient exists if the donor has an antigen which doesn't appear in the recipient.

Calculation of the number of HLA mismatches:

For the comparison of the HLA types between the donor and the recipient, the following steps should be done to calculate the number of HLA mismatches:

1. If the entry for a locus is a numeric code and a dash (or missing), then the dash for that locus is to be replaced (for calculation only) by the numeric code (homozygote).
2. The following rules should be applied when calculating the number of mismatches within a HLA A, B, and DR locus:
 - If both codes are missing in either the donor or recipient, the number of mismatches is unknown (missing)
 - If the two codes are non-missing and identical for the recipient and the donor (without regard to the order) or the donor is homozygote and the donor code matches either one of the recipient's codes then the number of mismatches is 0.

Examples:

Donor	Recipient	Mismatch
A1 A2	A2 A1	0
A2 A2	A2 A1	0

- If one code from the donor exists in the recipient but the other code is different between the donor and recipient or the donor has identical codes (homozygote) but they don't match either code in the recipient, then the number of mismatches is 1.

Examples:

Donor	Recipient	Mismatch
A2 A3	A2 A1	1
A2 A3	A2 A2	1
A2 A2	A3 A4	1
A2 A2	A1 A1	1

- If the donor is not homozygote and all codes are different between the donor and the recipient then the number of mismatches is 2.

Example:

Donor	Recipient	Mismatch
A1 A2	A3 A4	2

3. If the number of mismatches from any of the three loci are missing, then total number of HLA mismatches is missing. Otherwise the total number of HLA mismatches is the sum of the mismatches from the three loci.

